In a second experiment, an attempt was made to reproduce the posture of a non-rigid, female mannequin placed on the couch of a CT scanner. The first setup was done using only setup photos and room lasers, typically the only tools available for this type of “verification CT scan”.⁴ The second setup was performed using MixRT. In both cases, CT scans of the mannequin were acquired and registered with the initial, simulation CT scan using the torso as the area of focus. With the torso aligned in both registrations, the difference in arm position provides a way to assess the correctness of the overall posture. As seen in Figure 3, the MixRT setup outperforms the standard setup which showed a difference in arm position of 2 cm and further required a roll of 6-7 degrees in order to align the torso. In a real treatment scenario, this misalignment would require further manual correction, increasing the utilization of IGRT, overall setup time, and with no guarantee of a result matching that provided by MixRT. As previously noted, sub-optimal setups are often accepted, even with IGRT, due to the pressure to stay on schedule, minimize patient discomfort that can occur with prolonged time on the treatment couch, and the limitations of current methods. Thus, MixRT, with its ability to naturally guide both patient alignment and adjustment in real-time, provides a mechanism for increasing the overall accuracy of the treatment delivery and associated outcomes.

Figure 3. Preliminary accuracy of MixRT for non-rigid alignment demonstrating the elimination of roll and accurate arm placement compared to standard alignment methods. Left-to-right (axial, sagittal, coronal views).

5.) Specific Aims:

Perform a pilot study to assess the feasibility of MixRT. Feasibility will be based on the accuracy, overall setup time, and amount of IGRT needed when utilizing MixRT for patient setup in breast RT and in comparison, with current methods. Comparisons will be made between MixRT and 3-point alignment for photon treatment, and MixRT/IGRT versus IGRT alone for pencil beam scanning proton treatment. This data will establish viability and provide the framework for larger comparative effectiveness research studies and eventual FDA clearance.

6.) Research Plan:

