16 fractions is a common course of breast RT). For the second group, we will reverse the order, using MixRT for fractions 1-5 and 3-point alignment for fractions 6-10. In this way, each patient will serve as their own control. In all cases, patient alignment will be verified using CBCT which will be registered to the simulation CT by the treatment therapists using the standard clinical workflow. The magnitude of the resulting shift will be recorded. If further adjustment is necessary, the number of repeated CBCTs will be recorded along with the shift magnitude. All registrations will be reviewed by a board-certified radiation oncologist (one of the co-investigators) who will qualitatively assess the accuracy of the setup while blinded to the setup method. The process for mixed-reality alignment is noted below:

1. Identify the patient and initialize their hologram by detecting a QR-coded cube attached to the treatment device.
2. Setup the patient according to their setup photos, related immobilization devices (typically only an inclined breast board), and 3-point alignment. Further match the patient to their hologram as viewed through the HoloLens 2 device.
3. Utilize IGRT to verify proper alignment per protocol or departmental standards.
4. Make corrections as needed based on IGRT.
5. Repeat steps 1-3 if necessary.

For patients receiving proton therapy, setup typically includes routine CBCT, the challenges of which were previously discussed for non-rigid alignment including prolonged setup time and increased imaging dose. The primary goal of this sub-aim is thus to show that MixRT can reduce setup time and the amount of imaging dose in cases requiring CBCT alignment. To evaluate this, we will recruit an additional 12 patients scheduled to receive RT using a supine, pencil-beam scanning approach. As with 3DCRT/IMRT approach, we will divide patients into two groups using an alternating method and alternate the setup approach between fractions 1-5 and 6-10, reversing the order between the two groups. Setup time will be tracked from the moment the patient lies on the treatment couch to when the final position is confirmed by the therapist prior to treatment. Patient alignment will be verified/quantified in a similar manner as noted above.

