A window period of 2 additional fractions is permissible for the collection of study data. This window period is provided to allow a patient to remain on study through her 12th fraction of treatment if the patient is not able to receive the study intervention during one to two of her first 10 fractions.

To summarize, we intend to enroll 12 patients receiving either 3DCRT or IMRT and 12 patients receiving proton therapy. Within each modality, patients will be randomized into two groups using an alternating method. The order in which MixRT will be utilized will be reversed between the groups. The measured data will include registration accuracy (6 DoF shifts), setup time, and number of CBCT's utilized. Registration accuracy will be quantified using the image registration module that is used as part of the IGRT process. Setup time will be quantified using a stopwatch.

The number of CBCT's will be quantified via counting the number that are used during the setup process. Patients receiving photon IMRT receive daily CBCT as part of the standard of care. Thus, this investigation would likely not introduce additional imaging dose for these patients. For proton therapy CBCT is used weekly, and for 3DCRT it is not routinely used. Thus, this investigation would represent a marginal increase in the utilization of CBCT for these patients, up to 10 extra CBCT's nominally.

Setup during Verification CT

Radiotherapy patients at UFHPTI often receive repeat CT scans (verification scans) at periodic timepoints during the course of treatment to assess for anthropomorphic changes that could have dosimetric effect. Reproducing the posture from the initial CT simulation is critically important yet difficult to achieve due to the lack of real-time feedback. For patients who receive a verification CT (likely all proton patients), we will implement holographic alignment during this process and assess its accuracy in comparison to CT acquisition without the aid of holographic alignment. The procedure will be as follows:

1. Identify enrolled patients scheduled to receive a verification CT scan.
2. Setup patient without the aid of holographic alignment (standard method).
3. Acquire verification CT scan.
4. Dismantle the setup.
5. Utilize holographic alignment to correct patient posture. This involves a therapist wearing the HoloLens 2 device and viewing the patient's reference hologram overlaid the patient. The therapist will manually adjust the patient to match the hologram.

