- **Clearly state the nature of the experimental control (placebo, other treatment, historical) or the absence of a control:** Patients who receive verification CT, each patient will have their own control represented by the verification CT acquired without the use of holographic alignment. During the use of MixRT during patient setup, each patient will also have their own control represented by the sub-set of fractions where data is collected but holographic alignment is not employed.
- **Describe any randomization procedures:** Randomization is included during the use of MixRT guided patient setup where the patients are segmented into two groups. The order in which holographic alignment is introduced into the course of treatment is reversed for the two groups. The purpose is to control for setup variation which typically decreases after the first few fractions of treatment.
- **Describe completely all physical examinations, blood tests, x-rays, any special tests or procedures, surveys, questionnaires, and/or observations that will be used to obtain information about subjects:** No additional tests will be done that are outside the radiotherapy workflow. The study does include an increased utilization of specific aspects of the radiotherapy workflow, namely addition CT and CBCT acquisition.
- **Describe who will be responsible for obtaining the information and in what type of setting the information will be obtained:** Data will be collected during the course of radiotherapy treatment and during the acquisition of verification CT scans. Either the study investigators or trained radiation therapist will be responsible for collecting this data. The PI will serve as the primary data manager based on familiarity with the data.
- **Describe how these activities will answer the study questions:** The main question we seek to answer is whether mixed reality visualization is a feasible method for patient alignment in radiation therapy. To answer this question, we will collect relevant clinical data including registration error, registration time, and the amount of imaging used during the registration process. While we are not yet attaching power or a formal sample size structure to this data, we believe this data work together as our primary endpoints to answer the question of feasibility.

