The study also involves an increased utilization of CT and CBCT in order to quantify the difference in registration accuracy when using the mixed-reality method. Patients who receive a verification CT will receive 1-2 additional CT scans. During MixRT guided patient setup, patients will receive at least 0-10 additional CBCT scans (depends on modality). While it is routine for breast 3DCRT to employ planar kV imaging weekly as opposed to CBCT, it is not uncommon to utilize daily CBCT for difficult cases. Daily CBCT is also used for all cases where an IMRT approach is utilized. The dose from CBCT imaging is orders of magnitude less than the dose received during treatment, (approx. 1-2 mGy vs 45 Gy). According to the linear-no threshold model, there is non-zero risk of developing a radiation induced malignancy from any level of ionizing radiation. We believe the marginal increase in risk incurred through participation in this study, however, is low based on the limited amount of radiation delivered during CT and CBCT acquisition and the fact that these patients are already receiving high levels of ionizing radiation as part of their cancer treatment.

Only those Adverse Events related to the use of the HoloLens will be reported.

- **Identify potential financial risks study participants may incur:** None
- **Indicate any procedures, medications, tests, or therapies that study participants (or their insurer) will have to pay for. Are these considered standard therapies or are they specific to the research study?** None
- **Describe procedures to protect against or minimize potential discomforts and risks:** For individual cases, we will discontinue the use of the holographic alignment system if setup time is increased by more 30% during two consecutive sessions.

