- **Discuss why the risks to subjects are reasonable in relation to the anticipated benefits and in relation to the importance of the knowledge that may reasonably be gained:** We believe the marginal increase in risk of developing a radiation induced malignancy incurred through participation in this study is low. The immediate benefit to the study participants is that the additional CT and CBCT may improve the accuracy of their setups for instances in which these images are acquired. The long-term benefit for patients outside the study cohort will be the knowledge gained about the clinical use of mixed-reality for patient setup. We believe this method can improve the patient setup and alignment process and will eventually make the process faster and with the use of less ionizing radiation.

10.) Possible Benefits:

- **Describe the potential benefits to subjects or to others that may be reasonably expected to result from the research:** Based on prior study utilizing anthropomorphic phantoms, we anticipate that our patient alignment system will ultimately reduce setup time and the number of X-ray images used for alignment. By reducing setup time, we increase patient comfort and minimize the risk of patient movement during treatment. By reducing the number of X-ray images used, we reduce the amount of ionizing radiation the patient receives.
- **If there is no potential for direct benefits, you must state this in the Informed Consent Form:** Due to the fact that CBCT will be utilized for all study fractions, patients may benefit from a more accurate setup if CBCT was not standard of care for their treatment approach.
- **Will the research study benefit future populations?** Yes, possibly.

11.) Conflict of Interest:

- **Describe any real or potential conflict of interest you or any other investigators may have with regard to this research project:** The principal investigator has filed a provisional patent application in coordination with UF Innovate related to concept of aligning a patient via hologram.
- **When deciding whether a conflict may exist, consider the following:**
 - **Do you, the University of Florida, or any of the sub-investigators hold a patent or license for any material, object, or process used in this project?** No
 - **Is a patent or license pending or under consideration or is there any intention to file a patent application at a later date?** Yes.

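### Does a 30% setup-time stopping rule that names no reference time undermine the comparison between the two treatment orders?

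*Combined protocol and SAP*

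**What the plan says.** The rule sits in section 9, under the measures to limit discomfort and risk: for an individual patient, "we will discontinue the use of the holographic alignment system if setup time is increased by more 30% during two consecutive sessions". The section does not say whether the increase is over her own standard fractions, other patients' fractions or routine practice.

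Section 6 sets two orders. One group has standard setup in fractions 1-5 and MixRT in fractions 6-10. The other is the reverse: "For the second group, we will reverse the order, using MixRT for fractions 1-5 and 3-point alignment for fractions 6-10". Proton patients are split in the same way. The paragraph on the experimental control makes each patient's non-MixRT study fractions her control.

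On timing, the proton paragraph of section 6 states: "Setup time will be tracked from the moment the patient lies on the treatment couch to when the final position is confirmed by the therapist". On imaging, section 10 contains the phrase "Due to the fact that CBCT will be utilized for all study fractions". On routine practice section 6 says "For proton therapy CBCT is used weekly, and for 3DCRT it is not routinely used", with daily CBCT for IMRT. A few paragraphs before that, the same section describes CBCT as a usual part of proton setup.

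Setup time matters to the conclusion. Section 5 states "Feasibility will be based on the accuracy, overall setup time, and amount of IGRT needed when utilizing MixRT for patient setup in breast RT", and section 6 says of registration error, time and imaging "we believe this data work together as our primary endpoints to answer the question of feasibility". Section 7 plans means with 95% confidence intervals for each method and for their paired difference, and does not mention patients in whom MixRT is stopped. Section 6 also allows two extra fractions ("This window period is provided to allow a patient to remain on study through her 12th fraction of treatment") and up to 40 enrolled for about 24 needed.

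**The concern.** If the comparison is with the patient's own standard time, the rule can act in one order and not in the other. A standard-first patient brings five standard sessions to her first MixRT fraction; a MixRT-first patient brings none.

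If staff used routine times instead, the imaging would differ. Measured setup time runs to the confirmed position, so it includes the study CBCT, which routine 3DCRT setups mostly do not have. The study's own imaging would then count as slowing by MixRT, and patients in whom MixRT is no slower could lose it, more often in one order.

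A stop after session 2, 3 or 4 leaves three, two or one MixRT fractions unobserved, and the two-fraction window cannot supply them once MixRT has been withdrawn. If stopped patients were then left out of the analysis or replaced, the slow cases would be removed and MixRT would look faster than it is.

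**Working it through.** **Figure to reproduce.** None. The 30% has no derivation in the document, and section 7 calls the sample size a matter of practicality. The count adds up: 12 photon + 12 proton = 24. Alternation gives 6 per order in each modality, so 12 per order overall.

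**Own standard fractions before the first MixRT fraction.** Standard-first 5, MixRT-first 0. The first point of the concern is correct.

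**How much CBCT alone could add.** Let b be setup minutes without CBCT and c the CBCT minutes. The document gives no site times, so b = 6 and 11 are borrowed from the surface-guidance study cited in section 4, and c = 1 to 5 is assumed.

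- Reference without CBCT: increase = c/b. For b = 6: 1/6 = 17% to 5/6 = 83%. For b = 11: 1/11 = 9% to 5/11 = 45%. The 30% line is crossed above 0.3 x 6 = 1.8 min or 0.3 x 11 = 3.3 min.
- Reference with weekly CBCT: increase = (b + c)/(b + c/5) - 1. For b = 6: 7/6.2 - 1 = 13% to 11/7 - 1 = 57%. For b = 11: 12/11.2 - 1 = 7% to 16/12 - 1 = 33%.

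A routine reference could therefore mislead for 3DCRT. It would not for IMRT, where CBCT is daily. For proton the net effect cannot be worked out, because section 6 gives two descriptions of routine CBCT and no duration for other routine imaging.

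**Stop rates with no MixRT effect.** Simulation with log-normal times and five sessions per method; stop at the first two consecutive MixRT sessions above 1.3 x reference; 200,000 patients per order per cell. All inputs are assumed: patient CV of standard time 20/30/40%, patient CV of the MixRT/standard ratio 5/10/15%, session CV 10/15/20/25%, giving 3 x 3 x 4 = 36 cells. No time trend. The last column is rate x 12.

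| Order and reference | Stopped | Of 12 |
|---|---|---|
| Standard-first, own five-session mean | 0.3-14.1% | 0-1.7 |
| MixRT-first, site average with the same imaging | 10.1-21.9% | 1.2-2.6 |
| MixRT-first, routine average without CBCT, CBCT adding 10-30% | 20.3-48.4% | 2.4-5.8 |
| MixRT-first, own first MixRT session | 1.4-18.9% | 0.2-2.3 |

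Within a cell, the MixRT-first minus standard-first difference is +2.3 to +19.8 points with the same-imaging average, +11.5 to +47.6 with the routine average, and -4.5 to +8.6 with the own first session.

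**What a stop removes.** The rule needs two sessions, so a stopped patient keeps at least two MixRT fractions, and her paired difference can still be computed once she has standard fractions. A trigger at session 5 removes nothing; such triggers are 14-28% of the own-mean stops and 3-17% of the site-reference stops. Under the site references 41-85% of no-effect stops come at session 2. The price is precision: at a session CV of 25%, the standard error of her MixRT mean rises from 25/√5 = 11.2% to 25/√2 = 17.7%.

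**Effect on the time result.** Shift in (MixRT - standard)/standard, orders pooled, over all the references above including the routine one:

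| True MixRT effect | Recorded fractions kept | Stopped patients excluded or replaced |
|---|---|---|
| 10% faster | 0 to +1.1 points | 0 to -4.2 |
| None | 0 to +1.7 | 0 to -6.8 |
| 20% slower | +0.3 to +2.8 | -1.4 to -14.7 |

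On an 11-minute setup, +2.8 points is 0.028 x 11 = 0.31 min and -14.7 points is 0.147 x 11 = 1.62 min. On a 6-minute setup they are 0.17 and 0.88 min. Section 7 sets the paired time difference against 5 minutes.

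**The case for a change.** The best case for a change is that this rule protects patients and, as written, two therapists could apply it differently. Stops are also evidence on feasibility, so a rule that fires unequally by order blurs that evidence, and a few sentences would cure it. Even with matched imaging the orders can differ by up to 19.8 points, or 0.198 x 12 = 2.4 patients of 12. A time trend could widen the gap: section 6 expects setup variation to fall after the first fractions, and section 9 accepts that MixRT may be slower at first. In a separate simulation with session CV 25% and early fractions 0-20% longer, no-effect triggers were 1-10% for standard-first patients against their own mean, and 5-31% for MixRT-first patients against a reference with the same imaging.

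The missing reference time stands, as does the likelihood of unequal stops. Two things do not. First, the rule does not contradict the order reversal or the added CBCT: the routine comparator that yields the highest stop rates appears nowhere in the document, and other patients' standard study fractions could serve both orders once some exist. At the very start there may be none. Second, exclusion or replacement is an inference. The ceiling of 40 says nothing about stopped patients, the fraction window concerns missed sessions, and section 7 gives no ground for dropping a patient who has data under both methods.

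**Conclusion.** No change to the plan follows. The document leaves one detail open, the time against which the 30% is judged, and says nothing special about stopped patients. The analysis in section 7, run on the fractions recorded, is the natural reading. It leaves a shift of about 0 to +3 points, against MixRT and so conservative for a claim that it saves time, in a pilot that claims no power. Setup time, shifts and CBCT counts are kept for each patient, so curtailed MixRT blocks can be tabulated by session, order and modality without new data.

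The size rests wholly on assumed CVs and CBCT times and shows direction only. The shift was computed without a time trend; a learning effect would make it larger, by an amount not established here. The conclusion would differ if stopped patients were excluded or replaced and MixRT were appreciably slower, where the bias could reach -14.7 points.

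The two descriptions of routine CBCT for proton patients in section 6 do not agree and must be reconciled by the investigators. Which time serves as the reference in section 9 is likewise for them, and no reference or threshold is suggested here. Neither point alters the statistical analysis.
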